2. ADEQUACY OF PROTECTION AGAINST RISKS

a. Recruitment and Informed Consent

This information is listed on the eIRB website.

b. Protection against Risk

The following risks are present with this study: Risk of skin irritation, risk of discomfort, risk of slightly decreased heart rate, and risk of loss of confidentiality.

Risk of skin irritation: we will monitor the skin on the inner aspect of the left ear before and after each session, and will switch to the right ear if redness is present, and decrease the stimulation if redness persists.

Risk of discomfort: We expect to be able to use the pain ratings scales to identify the perception of tingling versus pain with taVNS in these infants. We will use facial expression change, fidgety movements and infant behavioral discomfort using our standard neonatal pain scale (NIPS) with the bedside nurse at the start and after 5 minutes of taVNS, at 10 minutes and at the end of treatment. We will protect against the risk of discomfort by close monitoring and by the determination of perceptual threshold using the protocol outlined above.

We will hold the treatment for a NIPS score of >3 , until discomfort subsides, and resume at a lower stimulus level if this level of discomfort recurs. We do not expect the infant to cry at this level, but show discomfort in brow furrowing, grimace, etc. Feeding is generally comforting for infants, and we expect to see minimal pain response to treatment. Infants are fed sidelying in the nursery. We will position the baby so that the left ear is facing up, and we can monitor the site and pain without disturbing the feeding process unduly.

Risk of slightly decreased heart rate: we will monitor HR, respiratory rate and oxygen saturation continually during the feeding to monitor these physiologic responses to taVNS-paired feeding. The infants' vital signs are constantly monitored as standard of care while in the nursery. We will print out values at baseline, and changes with feeding and taVNS-paired feeding. Normal heart rate is 120-170 beats per minute in preterm infants feeding, and 110-140 bpm in term HIE infants. As HR usually accelerates with motor activity of feeding, we do not expect significant bradycardic HR changes during the 'on' pulse. However, if the HR decreases to <100 bpm during 'on' pulse, or if HR rebound is >190 bpm during 'off' pulse, we will hold treatment and start again at a lower stimulation level.

Risk of loss of confidentiality: We will assign study numbers to each participant, keep CRF and consent forms in locked cabinets in locked offices. Database files with names and contact information will be password protected and stored on the MUSC Pediatric server. All other data files related to this study will be identified by participant number only, without link to standard identifiers. We will publish the aggregate data only. MRI files are stored by participant study number and date of scan.

3. POTENTIAL BENEFITS OF THE PROPOSED RESEARCH TO THE SUBJECTS AND OTHERS

taVNS paired with oromotor feeding training may enhance feeding skills, and enable the infants to learn this task more quickly and be discharged from hospital sooner. The treatment could potentially help avoid placement of a G-tube, but we will not be able to determine this from this dose-finding study. The treatment may also help with development of other motor skills, which we will assess by neurodevelopmental tests. We may also discover that taVNS-paired feed improves swallowing function, but even if we do not show any change in swallowing function, this data will support the safety of taVNS in neonates and infants. However, there may be no direct benefit to the participant, but we will gain knowledge about taVNS in infants, and strategies to improve oromotor skill training.

4. IMPORTANCE OF THE KNOWLEDGE TO BE GAINED

This trial could demonstrate the concept of “targeted plasticity” that could be used to enhance deficient networks in the preterm neonatal central nervous system. Behaviors integral to development such as feeding are impaired in this cohort, and if we can accelerate the learning of this behavior, we would greatly impact the recovery times and growth abilities of preterm or injured neonates. A positive connection between taVNS and learned motor function at such a critical time of development would contribute significantly to the field of neuronal plasticity and learned behaviors in neonates. If taVNS is shown to improve swallowing function, then this research may open up an entirely new treatment modality for these and other patients, such as post-stroke patients, who have swallowing problems.

5. SUBJECT SAFETY AND MINIMIZING RISKS (Data and Safety Monitoring Plan)

Introduction

The participants who receive active taVNS involved with this proposal will be neonates whose participation is agreed to by their guardians in written consent. The principal investigator will be responsible for monitoring the safety of the proposed experiments. She will also execute the Data Safety Management (DSM) plan and provide any necessary progress reports to the IRB, including but not limited to subject demographics, recruitment rates, retention rates, quality assurance issues, and adverse events or significant adverse events.

Data and Safety Monitoring Plan

[name] or her designee, should she be unavailable, will be responsible for reporting all unanticipated problems or AEs to the IRB. The PI will be present for each patient and record AE's real time. [name] will be responsible for reporting any unanticipated device-related AE's to FDA. All screening data will be kept in a binder in the locked office in [name] office. Screening data collected from participants who do not qualify for the study will be securely destroyed.

[name], who is a board certified neurologist and psychiatrist, and [name] will oversee the use of taVNS. [name] will also personally attend the sessions to monitor safety and adverse events.

An independent Safety Monitoring Committee (SMC) will be formed to advise the study investigators. The SMC will review and evaluate accumulated study data to ensure safety. They also will make recommendations concerning continuation, modification, or termination of any of the taVNS studies. It will be composed of [name], neonatologist; [name], MUSC associate professor and assistant provost with extensive VNS, TMS, and tDCS experience. [name], OT PhD, infant feeding expert, will be available to discuss subjective and objective measures of infant response during the taVNS experiments. [name], clinical OT and infant feeding expert, is not involved with the study, but will be giving many of the feeds during the tVNS sessions, and may also be called upon for impressions of safety and infant response, if the safety committee requires it.

Data will be discussed after the first five infants, and then again after 10 infants. The SMC will be notified immediately of any and all SAE's. We will report to the IRB the number of treatments held for

HR or redness, discomfort.

[name] will obtain informed consent, during which participants' guardians are fully advised on the research procedures to be used, the amount of time required of them, the possible risks and benefits of the procedures, their right to refuse their infant's participation in the study without prejudice, their right to terminate participation of their infant at any moment without prejudice, and the name and telephone number of the principal investigator.

Electronic Consent will be used for situations when the parent (or Legally Authorized Representative) is at another hospital and cannot travel to MUSC to provide consent in person. We will use the approved REDcap system to obtain consent. [name] or other approved study personnel will go over the entire consent document on the phone with the parent to ensure comprehension and to confirm identity. Parent will be given a copy of the completed, signed consent form in person or by email or fax.

Legal guardians will give informed consent. However, the Department of Social services may have custody of infant, but require the parent or foster parent to consent for all medical procedures.

Regarding confidentiality, subjects' guardians are informed that the information they provide, as well as participation in the study, will be kept strictly confidential, with access limited to the research staff. All paper records (consents, CRFs, study tools) will be kept in [name] locked office, in a locked cabinet. The identity of subjects in databases will be protected with alphanumeric codes. All data will be kept in locked file cabinets or on secure servers designed for use and access by Brain Stimulation and Neonatology Lab members only.

*Clinical Trials

Unless required by a funding agency, this study will not be registered on clinicaltrials.gov, as it will be considered a Phase 0 trial, used for assuring safety and feasibility of the taVNS-paired feeding treatment. The potential for intellectual property development and patent application by MUSC will preclude disclosure of this invention.

F. REFERENCES/LITERATURE CITATIONS

1. Kilgard MP. Harnessing plasticity to understand learning and treat disease. *Trends in neurosciences*. 2012;35(12):715-22.
2. Dawson J, et al., Safety, Feasibility, and Efficacy of Vagus Nerve Stimulation Paired With Upper-Limb Rehabilitation After Ischemic Stroke. *Stroke*. 2016 Jan;47(1):143-50.
5. Rutecki P. Anatomical, physiological, and theoretical basis for the antiepileptic effect of vagus nerve stimulation. *Epilepsia*. 1990;31(s2):S1-S6.

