Up to 40 preterm/HIE neonates will be enrolled in this prospective, open-label safety and feasibility trial, with a dose response. The experimental paradigm consists of 2 to 3 weeks of once or twice daily taVNS-paired feeding.

Our control group was investigated by Drs. [name] and [name] at MUSC, who have researched all infants failing feeding and getting Gastrostomy tubes in our nurseries over the past 5 years. We can compare our data to this historical group at our own institution.

All consented participants will receive the active stimulation condition.

taVNS Stimulation (in Detail)

After obtaining consent and describing this procedure to the parents and all members of the baby's care team, we will first, with a 500 μ s, 25Hz pulse, gradually increase the intensity of the TENS unit until the baby can first feel something in their ear. We will use the facial expression change and fidgety movements to determine when the infants feel the stimulation. This intensity will be recorded as the perceptual sensory threshold. The stimulation intensity we will use for this study on taVNS-paired feeding is a small decrement from the perceptual sensory threshold for each infant (-0.1mA), a point at which they should not react to the stimulation. We will retest the sensory threshold before every session.

Determination of Perceptual Threshold

1. Electrode clip will be placed on the left tragus in an enrolled infant at rest. Starting at 0.2mA at 25Hz, we will deliver 5 seconds of pulses, and increase by 0.1mA until the perceptual threshold is achieved by observation of the infant's facial expression, fidgety movements, or NIPPS score. This will be termed the perceptual threshold.
2. We will then deliver this level of microcurrent while the infant is feeding on the first day to determine if the perceptual threshold changes with feeding. Current will then be held constant while pulse width and frequency will be set at 500us and 25Hz, respectively.

3. Finally, we will decrease the microcurrent by 0.1mA *below the perceptual threshold* and administer this taVNS treatment during the feeding and deliver this only while the infant is actively sucking from the bottle.
4. The total duration of this 'on-and-off' taVNS stimulation treatment will continue for 30 minutes or the duration of the feed.
5. We may manually trigger the taVNS stimulation or place a gel EMG electrode over the temporomandibular joint area to trigger the taVNS impulse.

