1. RISKS TO THE SUBJECTS

The human subjects involved in this research will be preterm neonates or infants with critical illnesses that preclude oral feeding, such as HIE. Inclusion criteria involves 2 main groups. The first is comprised of typical pre-term, high risk neonates who are in the convalescent near and post-term period and learning to po feed. The second is comprised of neonates that present after severe medical illnesses or brain injury. In both cases, the infants can only be enrolled if they are stable, not making progress with OT training, and are in discussion for Gtube placement. Participants will be excluded if they have major unrepairs congenital abnormalities that limit volume of feeds, cardiomyopathy, significant autonomic instability, such as repetitive, unresolved bradycardia or apnea, or use a continuous positive airway pressure (CPAP) device or other form of high respiratory support preventing them from breathing without assistance.

Targeted/Planned Enrollment Table

Total Planned Enrollment: 40 babies (active)

TARGETED/PLANNED ENROLLMENT: Number of Subjects receiving active taVNS			
Ethnic Category	Sex/Gender		
	Females	Males	Total
Hispanic or Latino	4	5	9
Not Hispanic or Latino	15	16	31
Ethnic Category: Total of All Subjects*			

Racial Categories			
American Indian/Alaska Native			
Asian			
Native Hawaiian or Other Pacific Islander			
Black or African American	8	7	15
White	12	13	25
Racial Categories: Total of All Subjects*	20	20	40

*The “Ethnic Category: Total of All Subjects” must be equal to the “Racial Categories: Total of All Subjects”.

Volunteers of all ethnicities and racial categories will be accepted into this study protocol. No preference will be given based on race, gender or ethnicity. No vulnerable populations or special classes of subjects will be considered for participation.

b. Sources of Materials

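### No safety-committee review is scheduled after the tenth of up to 40 infants, and none is tied to twice-daily stimulation

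*Combined protocol and SAP*

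**What the plan says.** Section E.5 (Data and Safety Monitoring Plan) sets up an independent SMC that advises the investigators and recommends whether the work should carry on, change or stop. Its general task has no dates: "The SMC will review and evaluate accumulated study data to ensure safety". The only dated reviews are these: "Data will be discussed after the first five infants, and then again after 10 infants". The one stated trigger to the committee outside those dates is a serious event: "The SMC will be notified immediately of any and all SAE's".

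Non-serious safety data are routed elsewhere. The same section says "We will report to the IRB the number of treatments held for" heart rate, redness or discomfort, and gives no frequency. It also says that the investigator or a designee "will be responsible for reporting all unanticipated problems or AEs to the IRB", and that adverse events are recorded as they happen in each infant.

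On size and dose, Section D (Study Design) says "Up to 40 preterm/HIE neonates will be enrolled in this prospective, open-label safety and feasibility trial, with a dose response". The enrolment table in Section E.1 plans for 40 infants, all on active stimulation. Treatment is given once or twice daily, and the Data Analysis part of Section D compares the two schedules on feeding outcome. No allocation method, order or group size is given.

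**The concern.** Safety and feasibility are the main purpose of this trial, and Section B concedes that the investigators do not yet know what stimulus strength the infants will perceive. The events most likely to be informative are therefore the non-serious ones: sessions held for a heart-rate change, for a pain score above the limit, or for skin redness. Both dated SMC reviews fall in the first quarter of maximum enrolment. If holds became more frequent later, or clustered among infants treated twice daily, no scheduled meeting would put that pattern before the one body that the plan calls independent.

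The pause rule at the start of Section D does not fill this gap. It requires the IRB to be told before the next infant is enrolled, but only for events that are serious or absent from the consent form. Section E.1.c says that irritated skin, discomfort and a small fall in heart rate are already in the consent form. Unless serious, they do not trigger the pause. In any case, that rule leads to the IRB and not to the SMC.

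**Working it through.** The plan contains no sample-size, power or stopping calculation, so there is no figure of its own to reproduce. The check has three parts.

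**1. Share of infants entering after the last scheduled review.** Inputs: N = 40 (Section D ceiling; Section E.1 table) and last review at 10 infants (Section E.5). Formula: (N − last review)/N.

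- N = 40, last review at 10: (40 − 10)/40 = 30/40 = 75%.
- N = 40, second review ten infants after the first, so at 15: (40 − 15)/40 = 25/40 = 62.5%.
- If fewer enrol, last review at 10: N = 30 gives 20/30 = 67%; N = 20 gives 10/20 = 50%.

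**2. What a review can exclude.** With no infant affected among n, the exact two-sided 95% upper limit on the proportion affected is 1 − 0.025^(1/n). The chance of at least one affected infant among n, for a true per-infant rate p, is 1 − (1 − p)^n. The documents give no event rates, so p = 5% and p = 10% are assumptions for illustration.

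| Infants reviewed | Upper limit if none affected | At least one case, p = 5% (assumed) | At least one case, p = 10% (assumed) |
|---|---|---|---|
| 10 | 1 − 0.025^(1/10) = 30.8% | 1 − 0.95^10 = 40% | 1 − 0.90^10 = 65% |
| 20 | 1 − 0.025^(1/20) = 16.8% | 64% | 88% |
| 30 | 1 − 0.025^(1/30) = 11.6% | 79% | 96% |

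So for an event affecting 5% of infants, the chance that the last scheduled review has seen no case is 100% − 40% = 60%. For a 10% event it is 100% − 65% = 35%.

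**3. Whether twice-daily infants are covered.** This depends on an order that the plan does not state, so two cases bracket it.

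- If once-daily infants come first and number at least 10, no twice-daily infant falls within the reviews at 5 and 10.
- If 20 of 40 infants are treated twice daily in random order (an assumption), the chance of none among the first 10 is C(20,10)/C(40,10) = 0.00022, about 0.02%.

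**The case against.** The strongest reply is that safety oversight does not stop at infant 10. The investigator is responsible for safety monitoring and records events in every infant. Adverse events and held treatments go to the IRB throughout, and hold rules operate within each session. The SMC's task of reviewing accumulating data has no end date, so the two dated reviews can be read as fixed early points within a continuing remit. The committee only advises, and those whom it advises already see the events as they occur.

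Most of this stands, and it limits the point. A reader might infer that non-serious safety data go unreviewed for three quarters of the trial. The documents do not support that, because the investigator and IRB routes cover every infant. Nor do they bar the SMC from seeing hold counts. They simply give no date, trigger or data package that would bring those counts to it after infant 10.

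A reader might also infer that the whole twice-daily group escapes committee review. That is one possibility under an unstated order, and under random order with equal groups it is very unlikely.

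A further objection is that holds arise per session. Two weeks once daily is 14 sessions and three weeks twice daily is 42, so ten infants treated every day contribute 140 to 420 sessions. That is far more information on the rate per session, although sessions within an infant are correlated. It does not change the limit on the proportion of infants affected, which rests on the number of infants.

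Finally, nothing in the documents requires reviews at exactly 20 and 30. They are a reasonable spacing, not a standard.

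**Conclusion.** The point holds as a gap in scheduled independent review, not as an absence of safety oversight. At the ceiling of 40, 30 infants (75%) enter after the last dated SMC review, or 25 (62.5%) on the other reading of the second date. The share falls if fewer are enrolled. These counts take the review dates as numbers of infants enrolled; the plan does not say whether enrolment or completion is meant.

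A review of 10 infants with none affected still leaves a proportion of up to 31% compatible with the data. The detection chances of 40% and 65% rest on the assumed rates of 5% and 10%. What remains open on dose is narrower: no review is tied to twice-daily stimulation, and without a stated order nobody can tell whether the early reviews include it.

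This is an inexpensive improvement that the sponsor should make. It is not a flaw that undermines the trial.

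**What to change.** In Section E.5, keep the reviews at 5 and 10 infants and add scheduled SMC reviews at about 20 and 30. State that one review will include the first five infants treated twice daily, with a separate meeting only if the other dates do not cover them. Say whether the second review is at the tenth infant or ten infants after the first.

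At each review, give the SMC the counts of treatments held for heart rate, redness and discomfort that are already collected for the IRB, tabulated per infant and by once- or twice-daily schedule. The per-infant split is not described in the plan, so it is a small addition.

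The cost is two or three short extra meetings of an existing committee and one simple table per meeting. No treatment, hold or dose rule changes.

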their collaborators include: transcranial magnetic stimulation (TMS), vagus nerve stimulation (VNS), transcranial direct current stimulation (tDCS), electroconvulsive therapy (ECT), deep brain stimulation (DBS) and epidural cortical stimulation (epCS). ECT, VNS and TMS are clinical services offered within the BSL. BSL researchers at MUSC were the first in the world (in 1998) to implant VNS devices in patients with major depression who had not adequately responded to traditional antidepressants.

I. INVESTIGATOR BROCHURE

N/A

J.APPENDIX

N/A
